## ABBREVIATIONS

$\lambda_z$	Terminal elimination rate constant
%CV	Percent coefficient of variation
AE	Adverse Event
ADA	Anti-drug antibody
aPTT	Activated partial thromboplastin time
AUC 0-last	Area under the concentration-time curve from time zero to the last quantifiable concentration in plasma
AUC 0-∞	Area under the concentration-time curve from time zero extrapolated to infinity
β-hCG	Beta-Human Chorionic Gonadotropin
BMI	Body Mass Index
BP	Blood Pressure
CRA	Clinical Research Associate
CRC	Clinical Research Center
CRF	Case Report Form
cHMWK	Cleaved High Molecular Weight Kininogen
C max	Maximum Observed Plasma Drug Concentration
C1-INH	C1 Inhibitor
CHO	Chinese Hamster Ovary
CL/F	Apparent Clearance
CRO	Contract Research Organization
CV%	Coefficient of Variation
DMC	Data Monitoring Committee
EC	Ethics Committee
ECG	Electrocardiogram
EMA	European Medicines Agency
EU	European Union
FDA	Food and Drug Administration
FSH	Follicle Stimulating Hormone
GCP	Good Clinical Practice
HAE	Hereditary Angioedema
HBsAg	Hepatitis B Surface Antigen
HCV	Hepatitis C Virus

HIPAA	Health Insurance Portability and Accountability Act
HIV	Human Immunodeficiency Virus
ICH	International Conference on Harmonisation
INR	International Normalized Ratio
IgG1	Immunoglobulin G Subclass 1
IRB	Institutional Review Board
IRT	Interactive Response Technology
Ki	Inhibition Constant
MHLW	Ministry of Health, Labor and Welfare
LLOQ	Lower limit of Quantification
Mg	Milligram
mL	Milliliter
mmHG	Millimeters Mercury
PD	Pharmacodynamic
PK	Pharmacokinetic
PMDA	Pharmaceuticals and Medical Devices Agency
PR	Time elapsed from P wave to R wave in an electrocardiogram
PT	Prothrombin Time
QRS	Measure of time for the 3 main deflections in an electrocardiogram
QT	Measure of time between the start of the Q wave and the end of the T wave in an electrocardiogram
QTcB	Measure of time between the start of the Q wave and the end of the T wave using Bazett's formula in an electrocardiogram
QTcF	Measure of time between the start of the Q wave and the end of the T wave using Fridericia's formula in an electrocardiogram
RR	The time between heart beats in an electrocardiogram
SAE	Serious Adverse Event
SAP	Statistical Analysis Plan
SC	Subcutaneous
SD	Standard Deviation
TEAE	Treatment-Emergent Adverse Event
$t_{1/2}$	Terminal half-life
US	United States
$V_{d_{z/F}}$	Apparent Volume of Distribution

## STUDY SYNOPSIS

Protocol number: SHP643-101	Drug: Lanadelumab
Title of the study: A Phase 1, Open-label Study to Evaluate the Pharmacokinetics, Safety and Tolerability, and Pharmacodynamics of a Single Dose of Lanadelumab Administered Subcutaneously in Healthy Adult Japanese Subjects and Matched Healthy Adult Caucasian Subjects	
Number of subjects (total and for each treatment arm): A total of 32 healthy adult, male and/or female subjects will be enrolled into the study, comprising 16 subjects of Japanese descent and 16 matched, non-Hispanic, Caucasian subjects. Assuming a 25% dropout rate, approximately 24 subjects (12 from each race/ethnicity) are expected to complete the study. Study subjects who withdraw or discontinue early may be replaced at the discretion of the sponsor. Non-Hispanic, Caucasian subjects will be matched to subjects of Japanese descent based on sex (1:1 male: male, female: female), age ( $\pm 5$ years), and body mass index ( $\pm 15\%$ ). 

• The subjects of Japanese descent will receive one single 300mg subcutaneous (SC) dose of lanadelumab.

• Matched, non-Hispanic, Caucasian subjects will receive one single 300mg SC dose of lanadelumab.

	
Investigator(s): PPD [REDACTED], MD	
Site(s) and Region(s): West Coast Clinical Trials [name]	
Study period (planned): 2018	Clinical phase: 1
Objectives: Primary: To evaluate the pharmacokinetic (PK) properties of lanadelumab administered as a single SC dose of 300 mg in healthy adult volunteer subjects of Japanese descent and matched non-Hispanic, Caucasian healthy volunteer subjects. Secondary: To assess the safety and tolerability of lanadelumab administered as a single SC dose of 300 mg to healthy adult volunteer subjects of Japanese descent and matched non-Hispanic, Caucasian healthy volunteer subjects. Endpoints corresponding to the primary and secondary objectives are defined in the endpoints and statistical analysis section of this Synopsis.	
Rationale: This study is being conducted to characterize the PK and pharmacodynamic (PD) properties of lanadelumab and to evaluate the safety and tolerability of lanadelumab administered as a single SC dose of 300 mg in healthy subjects of Japanese descent and in matched healthy non-Hispanic, Caucasian subjects. The results of this study will be used to support the selection of the dosing regimen for a Phase 3 study conducted in Japanese patients with hereditary angioedema (HAE). The Japanese regulatory agencies, Pharmaceuticals and Medical Devices Agency (PMDA) and the Ministry of Health, Labor and Welfare (MHLW) require evidence that current data in non-Japanese subjects can be extrapolated to the Japanese population. For this reason, the SHP643-101 study is designed to characterize PK and PD profiles, as well as to evaluate the safety and tolerability of lanadelumab in Japanese and matched non-Hispanic, Caucasian healthy volunteer subjects.	

**Investigational product, dose, and mode of administration:**

- Lanadelumab, 300mg SC injection into the abdomen.
- Lanadelumab is a recombinant, fully human immunoglobulin G subclass 1 (IgG1), a kappa light chain monoclonal antibody expressed in Chinese Hamster Ovary (CHO) cells. Lanadelumab is a potent ( $K_i = 125 \text{ pM}$ ) inhibitor of the proteolytic activity of plasma kallikrein. Lanadelumab drug product is a colorless to yellow, sterile, preservative-free solution, appearing either clear or with slight opalescence. The active ingredient, lanadelumab, is formulated using the following compendial components: 30mM sodium phosphate dibasic dihydrate, 19.6mM citric acid, 50 mM histidine, 90 mM sodium chloride, 0.01% Polysorbate 80. Each vial contains a nominal concentration of 300 mg in 2 mL (150 mg/mL) solution. A 300 mg, single SC dose was selected for this study. For each 300 mg dose of lanadelumab, each subject will receive a total of 2 mL, which will be administered in a single 2 mL SC injection. This study is open-label and does not require the use of a placebo.

**Methodology:**

This study is a Phase 1, open-label, matched-control, single-dose, single-center study to evaluate the PK, safety and tolerability and PD of lanadelumab administered to healthy adult volunteer subjects of Japanese descent and matched non-Hispanic, Caucasian healthy adult volunteer subjects. A total of 32 subjects between the ages of 18-55, inclusive will be enrolled: 16 non-Hispanic Caucasian subjects and 16 subjects of Japanese descent. Assuming a 25% dropout rate, approximately 24 subjects (12 subjects from each race/ethnicity) are expected to complete the study. Non-Hispanic Caucasian subjects will be matched to Japanese subjects based on sex (1:1 male: female), age ( $\pm 5$  years), and body mass index (BMI) ( $\pm 15\%$ ). For example, a Japanese male, age 40 years, and BMI of  $22 \text{ kg/m}^2$  will be matched with a Caucasian male, age  $40 \pm 5$  years (35-45 years [inclusive]), and BMI of  $22 \pm 15\%$  ( $18.7\text{-}25.3 \text{ kg/m}^2$ ).

All subjects will receive a single dose of 300 mg of lanadelumab administered by SC injection into the abdomen.

The study duration will be comprised of a 28-day screening period, one 5-day in-house treatment period, and multiple out-patient visits (Day 7 [ $\pm 1$  day], Day 14 [ $\pm 1$  day], Day 21 [ $\pm 1$  day], Day 28 [ $\pm 1$  day], Day 42 [ $\pm 2$  days], Day 56 [ $\pm 2$  days], Day 84 [ $\pm 3$  days] and Day 112 [ $\pm 3$  days]) after the single dose of investigational product is administered. The maximal total duration of study participation for a subject is approximately 140 days if the maximal screening, treatment, and out-patient durations are used.

Screening Period

Screening will occur within 28 days of the first dose. Subjects will be admitted to the Clinical Research Center (CRC) on Day -1.

In-House Confinement Treatment Period

- On Day 1, all subjects will receive lanadelumab as a single 300 mg SC injection into the abdomen.
- All subjects will remain in the CRC until completion of the 96 hour postdose PK sample on Day 5.

Assessments

- Serial blood samples for PK analysis will be collected for the determination of plasma lanadelumab concentrations from Day 1 predose and up to 96 hours post dose during the in-house confinement period and up to Day 112 during the out-patient visit period. These blood samples will be collected according to the Schedule of Assessments.

- Safety and tolerability including anti-drug antibodies (ADAs) will be determined through assessment of treatment-emergent adverse events (TEAEs) and vital signs, electrocardiogram (ECG) findings, and clinical laboratory evaluations on Day 1 predose and up to 96 hours postdose during the in-house confinement period and up to Day 112 during the out-patient visit period according to the Schedule of Assessments.
- Serial blood samples for PD analysis will be collected for kallikrein activity and for cleaved high molecular weight kininogen (cHMWK) from Day 1 predose and up to 96 hours postdose during the in-house confinement period and up to Day 112 during the out-patient visit period. These blood samples will be collected according to the Schedule of Assessments.

#### Out-Patient Visit Period

Out-patient visits will be completed on the following Study Days:

- Day 7 ( $\pm$  1 day; ie, Day 6, 7, or 8)
  - Day 14 ( $\pm$  1 day; ie, Day 13, 14 or 15)
  - Day 21 ( $\pm$  1 day; ie, Day 20, 21 or 22)
  - Day 28 ( $\pm$  2 day; ie, Day 26, 27 28, 29, or 30)
  - Day 42 ( $\pm$  2 days; ie, Day 40, 41, 42, 43 or 44)
  - Day 56 ( $\pm$  2 days; ie, Day 54, 55, 56, 57 or 58)
  - Day 84 ( $\pm$  3 days; ie, Day 81, 82, 83, 84, 85, 86 or 87)
  - Day 112 ( $\pm$  3 days; ie, Day 109, 110, 111, 112, 113, 114 or 115)
- after the single dose of investigational product is administered. Refer to [Table 2](#) for complete details.

#### **Inclusion Criteria:**

1. Ability to voluntarily provide written, signed, and dated informed consent as applicable to participate in the study.
2. An understanding, ability, and willingness to fully comply with study procedures and restrictions.
3. Age 18-55, inclusive, at the time of consent. The date of signature of the informed consent is defined as the beginning of the Screening Period. This inclusion criterion will only be assessed at the first screening visit.
4. Subjects must be either:
  - a. A subject of Japanese descent born in Japan, who has resided outside of Japan for no longer than 5 years and is of Japanese parentage, defined as having 2 Japanese parents and 4 Japanese grandparents, all born in Japan
  - b. A non-Hispanic, Caucasian subject who has 2 non-Hispanic, Caucasian parents and 4 non-Hispanic, Caucasian grandparents
5. Male or non-pregnant, non-lactating female who agrees to comply with any applicable contraceptive requirements of the protocol or females of nonchildbearing potential.
6. Considered “healthy” by the investigator. Healthy status is defined by absence of evidence of any active or chronic disease following a detailed medical and surgical history, as well as a complete physical examination including vital signs, 12-lead ECG, hematology, blood chemistry, and urinalysis.

7. Body mass index between 18.5-33 kg/m^2, inclusive, with a body weight  $\geq$ 45 kg (99lbs). This inclusion criterion will only be assessed at the screening visit.
8. Willing and able to consume standardized meals during the confinement period of the study. All participants will be required to consume the identical meals on study days when serial PK and PD blood samples are collected.

**Exclusion Criteria:**

1. History of any hematological, hepatic, respiratory, cardiovascular, renal, neurological or psychiatric disease, gall bladder removal, or current or recurrent disease that could affect the action, absorption, or disposition of the investigational product, or clinical or laboratory assessments.
2. Current or relevant history of physical or psychiatric illness, any medical disorder that may require treatment or make the subject unlikely to complete the study, or any condition that presents undue risk from the investigational product or procedures.
3. Known or suspected intolerance or hypersensitivity to the investigational product, closely-related compounds, or any of the stated ingredients.
4. Significant illness, as judged by the investigator, within 2 weeks of the dose of investigational product.
5. Known history of alcohol or other substance abuse within the last year, per the investigator.
6. Donation of blood or blood products (eg, plasma or platelets) within 60 days prior to receiving the dose of investigational product.
7. Within 30 days prior to the dose of investigational product:
  - a. Have used an investigational product (if elimination half-life is  $<$ 6 days, otherwise 5 half-lives).
  - b. Have been enrolled in a clinical study (including vaccine studies) that, in the investigator's opinion, may impact this Shire-sponsored study.
8. Confirmed systolic blood pressure (BP)  $>$ 139mmHg or  $<$ 89mmHg, and diastolic BP  $>$ 89mmHg or  $<$ 49mmHg.
9. Twelve-lead ECG values (average of triplicate readings) demonstrating QTc  $>$ 450msec (males) or  $>$ 470msec (females) at the Screening Visit or Day -1.
10. Positive screen for drugs of abuse (i.e. amphetamines, benzodiazepines, barbiturates, cocaine, marijuana, opiates, phencyclidine) at Screening, or drugs of abuse or alcohol on Day -1.
11. Male subjects who consume more than 21 units of alcohol per week or 3 units per day. Female subjects who consume more than 14 units of alcohol per week or 2 units per day. One alcohol unit=1 beer or 1 wine (5oz/150mL) or 1 liquor (1.5oz/40mL) or 0.75oz alcohol.
12. Positive HIV, HBsAg, or HCV antibody screen.
13. Use of tobacco in any form (eg, smoking or chewing) or other nicotine-containing products in any form (eg, gum, patch, electronic). Ex-users must report that they have stopped using tobacco for at least 30 days prior to receiving the dose of investigational product.

14. Routine consumption of more than 2 units of caffeine per day or subjects who experience caffeine withdrawal headaches. One caffeine unit is contained in the following items: one 6oz (180mL) cup of coffee, two 12oz (360mL) cans of cola, one 12 oz cup of tea, and three 1oz (85g) chocolate bars. Decaffeinated coffee, tea, or cola are not considered to contain caffeine).
15. Current use of any medication (including over-the-counter, herbal, or homeopathic preparations; with the exception of stable hormonal replacement therapy or hormonal contraceptives). Current use is defined as use within 14 days of the dose of investigational product. See Section 5 (Prior and Concomitant Treatment) for a list of permitted medications.
16. Abnormal laboratory values considered clinically significant, as determined by the investigator at Screening or Day -1.
17. History of any clinically significant surgery or procedure within 8 weeks of receiving the dose of investigational product, as determined by the investigator.

**Maximum duration of subject involvement in the study:**

- Planned duration of screening period: 28 days maximum
- Planned duration of in-house confinement period: 5 days
- Planned duration of out-patient visit period: 107 days

**Endpoints and statistical analysis:**

Pharmacokinetic endpoint(s)/parameters:

- $C_{max}$ : Maximum observed plasma drug concentration
- $t_{max}$ : Time to reach  $C_{max}$  in plasma
- $AUC_{0-last}$ : Area under the concentration-time curve from time zero to the last quantifiable concentration in plasma
- $AUC_{0-\infty}$ : Area under the concentration-time curve from time zero extrapolated to infinity
- $\lambda_z$ : Terminal elimination rate constant
- $t_{1/2}$ : Terminal half-life
- CL/F: Apparent clearance
- $V_{d/F}$ : Apparent volume of distribution

Safety is the secondary objective of this study. Safety endpoint(s):

- Treatment-emergent adverse events: Number and percentage of subjects with TEAEs; severity; seriousness; causality; number of TEAEs.
- Clinical laboratory results (hematology, clinical chemistry, coagulation and urinalysis): Changes from baseline to post-baseline time points; clinically significant abnormal laboratory assessments.
- Other: Vital signs (including BP, pulse, body temperature), 12-lead ECG, and physical examination: Changes from baseline to post-baseline time points.
- Anti-drug antibodies

**Analysis populations/analysis sets:**

- Safety population (Safety Analysis Set), defined as all subjects who received at least 1 dose of lanadelumab (study drug). All safety analyses will be based on the Safety population/Safety Analysis Set.
- Pharmacokinetic population (PK Analysis Set), defined as all subjects who received at least 1 dose of lanadelumab and have at least 1 evaluable postdose PK concentration value. All PK analyses will be based on the PK population/PK Analysis Set).

**Statistical analysis:**

No statistical hypothesis testing is planned. Analysis details will be provided in the study Statistical Analysis Plan (SAP), which will be finalized prior to study database lock. Only descriptive analysis will be performed to evaluate all primary and secondary endpoints. Summaries will be presented by racial/ethnic group (Japanese vs. non-Hispanic Caucasians), and, if appropriate, by time point. All data, including derived data, will be presented in subject data listings, and all listings will include subject's sex, age, race/ethnicity, and BMI.

- No interim analysis or Data Monitoring Committee (DMC) is planned.

## STUDY SCHEDULE(S)

**Table 1: Schedule of Assessments**

Visit	Screening	In-House Treatment Period						Out-Patient Visits a / Early Discontinuation b
		-28 to -02	-1	1	2	3	4	
Study Day								
Informed consent	X							
Inclusion/exclusion criteria	X	X						
Demography and medical/medication history	X	X c						
Physical examination	X	X					X	X
Vital signs (blood pressure, pulse) supine d	X	X	X	X	X	X	X	X
Body temperature (oral)	X		X					X
Height, Weight and BMI e,f	X	X					X	X
Electrocardiogram (12-lead) d	X g	X g	X	X	X	X	X	X
Biochemistry h , hematology, and urinalysis	X	X		X			X	X
PT, aPTT, INR	X	X					X	X
HIV, HBsAg, and HCV antibodies	X							
Serum Pregnancy test (all females) d	X	X					X	X
FSH (females only)	X							
Urine drug and alcohol (breath test) screening i	X	X						X j
Investigational Product administration			X					
Pharmacokinetic blood sampling d			X	X	X	X	X	X j
Anti-drug antibody testing d			X					X
Pharmacodynamic blood sampling d			X	X	X	X	X	X j
Check-in to the CRC		X						
Discharge from the CRC							X	
In-house confinement		X	X	X	X	X		
Out-patient visits	X							X
Adverse events/serious adverse events	X	X	X	X	X	X	X	X
Concomitant medication	X	X	X	X	X	X	X	X

HBsAg=hepatitis B surface antigen; HCV=hepatitis C virus; HIV=human immunodeficiency virus

a There will be multiple out-patient visits on: Day 7 (± 1 day), Day 14 (± 1 day), Day 21 (± 1 day), Day 28 (± 1 day), Day 42 (± 2 days), Day 56 (± 2 days), Day 84 (± 3 days) and End of Study Day 112 (± 3 days), after the dose of investigational product is administered on Day 1. Refer to [Table 2](#) for complete details.

b In the event a subject is prematurely discontinued from the study or withdraws, every attempt should be made to complete these assessments.

c Medical history and medication history review only

d See [Table 2](#) for detailed collection time points

e Height will be recorded at the Screening Visit only

f BMI criteria for eligibility will be calculated at the Screening Visit.

g ECGs will be performed in triplicate at Screening and Day -1 only. Thereafter, all subsequent ECGs will be single recordings

h Thyroid function tests (TSH, T3, T4) will be collected as part of the biochemistry panel at Screening only.

i Drugs of abuse at screening, and drugs of abuse and alcohol (breath test) on Day -1 and at all out-patient visits.

j No PK or PD sample, or urine drug or alcohol screen should be collected for early discontinuation.

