## 4.5 Discontinuation of Subjects

A subject may withdraw from the study at any time for any reason without prejudice to their future medical care by the physician or at the institution. The investigator or sponsor may withdraw the subject at any time (eg, in the interest of subject safety). The investigator is encouraged to discuss withdrawal of a subject from investigational product with the medical monitor when possible.

If investigational product is discontinued, regardless of the reason, the early withdrawal evaluations listed in [Table 2](#) are to be performed as completely as possible. Whenever possible, all discontinued subjects should also undergo the protocol-specified follow-up (ie Day 112/ End of Study Visit). Comments (spontaneous or elicited) or complaints made by the subject must be recorded in the source documents. The reason for termination and date of stopping investigational product must be recorded in the case report form (CRF) and source documents.

Subjects who withdraw or discontinue early may be replaced (if needed) at the discretion of the sponsor, to ensure that approximately 24 subjects (12 from each race/ethnicity) complete the study.

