### **9.6 Sample Size Calculation and Power Considerations**

The planned sample size for this study is 32 subjects: 16 subjects of Japanese descent and 16 matched non-Hispanic Caucasian subjects.

Assuming a 25% dropout rate, the sample size ensures approximately 24 subjects (12 Japanese and 12 matched Caucasians) complete the study, and 24 subjects are evaluable for pharmacokinetic analysis purposes. The sample size is considered adequate for the primary and secondary objectives of the study and therefore adequate for providing reliable estimates of pharmacokinetic parameters.

The sample size was based on clinical judgment and precedent pharmacokinetic studies of similar design and similar subject population and not on statistical considerations such as study power. Subjects who prematurely discontinued the study, whether subjects are part of matched pairs or are not yet matched, may be replaced at the discretion of the study sponsor to ensure there are approximately 12 evaluable subjects in each racial/ethnic group for pharmacokinetic analysis purposes.

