12.1.3 Pharmacokinetic Parameters

The PK analysis will be conducted using Phoenix[®] WinNonlin[®] (Certara USA, Inc, Princeton, NJ) Version 6.4 or higher. Pharmacokinetic parameters will be determined from the lanadelumab plasma concentration-time data using non-compartmental analysis based on actual sampling times. All samples will be used in the PK analysis regardless of whether they are considered protocol deviations or not.

The PK parameters for lanadelumab will include, but may not be limited to:

- C_{\max} Maximum observed lanadelumab plasma concentration
- t_{\max} Time of maximum observed lanadelumab plasma concentration
- $AUC_{0-\text{last}}$ Area under the lanadelumab plasma concentration-time curve from time zero to the last quantifiable plasma concentration, calculated using the linear-up/log-down trapezoidal rule

In this method, the linear trapezoidal method of calculation is used for each incremental trapezoid and the log trapezoidal rule for each decremental trapezoid
- $AUC_{0-\infty}$ Area under the lanadelumab plasma concentration-time curve from time zero extrapolated to infinity
- λ_z First order rate constant associated with the terminal (log-linear) portion of the lanadelumab plasma concentration curve

- $t_{1/2}$ Terminal half-life
- CL/F Apparent clearance
- V_z/F Apparent volume of distribution

Body weight-adjusted AUC_{0-last} , $AUC_{0-\infty}$, C_{max} , CL/F, and V_z/F PK parameters will also be determined.

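### Both schedules bar PK and PD samples at the early-discontinuation visit; lifting the bar is a cheap way to shorten, though not remove, the truncation of early leavers' profiles

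*Protocol*

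**What the plan says.** - **The bar.** Protocol Table 1, footnote j: "No PK or PD sample, or urine drug or alcohol screen should be collected for early discontinuation". Table 2 footnote d says the same, and SAP 2.4 carries both footnotes unchanged. No reason is given.
- **What is still done at that visit.** Footnote b to the same column of Table 1 reads: "In the event a subject is prematurely discontinued from the study or withdraws, every attempt should be made to complete these assessments". The biochemistry, hematology, coagulation and ADA rows are marked there without the exemption.
- **How off-schedule samples are treated.** SAP 12.1.3 bases the non-compartmental analysis (NCA) on actual times and adds: "All samples will be used in the PK analysis regardless of whether they are considered protocol deviations or not". SAP 12.1.1 flags out-of-window samples and leaves them out of concentration summaries and mean plots.
- **Who is analysed.** The PK Set (SAP 4.3) keeps any dosed subject with one evaluable postdose concentration. Cmax, AUC0-last and AUC0-inf from this set enter the ANOVA in SAP 12.2.
- **How many may leave.** Protocol 9.6: "The planned sample size for this study is 32 subjects: 16 subjects of Japanese descent and 16 matched non-Hispanic Caucasian subjects", and "Assuming a 25% dropout rate, the sample size ensures approximately 24 subjects".
- **Later follow-up.** Protocol 4.5: "Whenever possible, all discontinued subjects should also undergo the protocol-specified follow-up (ie Day 112/ End of Study Visit"). It does not say whether PK or PD blood is drawn from a discontinued subject at Day 112.

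**The concern.** The visit already involves venepuncture, and the tubes left out are those for the primary (PK) and exploratory (PD) objectives. Dosing is complete on Day 1, so a concentration from a subject who later leaves the study still describes the studied dose.

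Without the exit sample, the profile ends at the last scheduled visit attended, and visits are two to four weeks apart after Day 28. AUC0-last is then cut shorter than it need be. The terminal slope, and with it half-life, AUC0-inf, CL/F and Vz/F, rests on fewer points. These subjects stay in the PK Set, and the SAP sets no minimum number of points for lambda-z, no limit on extrapolated AUC and no rule for truncated profiles in the ANOVA. If dropout timing or frequency differs between the ethnic groups, truncation also shifts the AUC0-last ratio.

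**Working it through.** **1. The plan's own figures.** 24 / (1 - 0.25) = 32 enrolled, and 12 / 0.75 = 16 per group, as stated. Expected leavers: 32 x 0.25 = 8, or 4 per group. PK samples: 6 in-house (predose, 8, 24, 48, 72, 96 h) + 8 out-patient = 14, matching protocol Table 3. Blood volume: 70 + 70 + 8.5 + 102 + 48 + 29.7 + 15 = 343.2 mL, also matching.

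**2. AUC captured, with and without an exit sample.** The documents give no half-life, so the following are assumptions: one compartment, first-order absorption with half-life 2 days, elimination half-life 7, 14 or 21 days, and an exit visit midway between two scheduled visits. Day n is n - 1 days after the dose. With k = ln 2 / elimination half-life and a = ln 2 / 2, the share of AUC0-inf observed by time t is

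F(t) = 1 - [a e^(-kt) - k e^(-at)] / (a - k).

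Example, half-life 14 days (k = 0.0495, a = 0.3466, a - k = 0.2971):
- Last sample Day 28 (t = 27): e^(-kt) = 0.2627 and the e^(-at) term is negligible. F = 1 - 0.3466 x 0.2627 / 0.2971 = 69.4%.
- Exit sample Day 35 (t = 34): e^(-kt) = 0.1857, so F = 1 - 0.3466 x 0.1857 / 0.2971 = 78.3%.

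| Last sample, exit sample | Half-life 7 d | 14 d | 21 d |
|---|---|---|---|
| Day 14, Day 17.5 | 61.8 to 72.8% (+11.0) | 38.9 to 48.5% (+9.6) | 28.2 to 35.9% (+7.8) |
| Day 28, Day 35 | 90.3 to 95.2% (+4.8) | 69.4 to 78.3% (+9.0) | 54.7 to 64.0% (+9.4) |
| Day 56, Day 70 | 99.4 to 99.8% (+0.5) | 92.3 to 96.2% (+3.8) | 82.0 to 88.7% (+6.7) |
| Day 84, Day 98 | 100.0 to 100.0% (+0.0) | 98.1 to 99.0% (+1.0) | 92.9 to 95.5% (+2.6) |

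Gains are taken before rounding. Applying the SAP's linear-up/log-down rule at the scheduled times lowers each share by up to about 1.6 points and leaves the gains unchanged. A Day 112 completer has F(111) = 100.0, 99.5 and 97.2%.

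**3. Terminal slope.** Assume a 15% residual CV. The relative SE of lambda-z is 0.15 / (k x sqrt(Sxx)), where Sxx is the sum of squared deviations of the sampling times.
- Half-life 14 days, samples on Days 14, 21 and 28: Sxx = 98, relative SE = 0.15 / (0.0495 x 9.90) = 0.31.
- Adding Day 35: Sxx = 245, relative SE = 0.15 / (0.0495 x 15.65) = 0.19.

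When the last scheduled sample is Day 14, the highest sampled value in this model is Day 7 at all three half-lives. The exit sample is then only the second point after the sampled peak.

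**4. Blood at the exit visit.** Using Table 3 volumes: 8.5 (biochemistry) + 4 (hematology) + 2.7 (coagulation) + 3 (ADA) = 18.2 mL already drawn. One PK and one PD sample add 5 + 5 = 10 mL. A discontinued subject misses later scheduled draws of the same kind, so the 343.2 mL total is not threatened.

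**The case against.** The bar is explicit, identical in both documents and contradicts no other instruction outright, and no planned estimate fails because of it. The design enrols 16 per group to keep about 12 and allows replacement. That protects the number of completers, but it does not lengthen the short profiles that remain in the PK Set.

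Several stronger readings are tempting, and the documents do not support them:
- **All eight leavers would benefit.** Eight is a ceiling. Protocol 4.5.1 lists loss to follow-up and withdrawal among the reasons for leaving, and such subjects may never attend an exit visit.
- **The exit sample is the only one that could extend the curve.** Section 4.5 asks leavers to return at Day 112, a scheduled PK visit. The footnote does not expressly forbid PK then; it leaves the matter unclear.
- **It rescues lambda-z in a Day 14 leaver.** It supplies only two points after the sampled peak, or three if the peak itself is counted.
- **The ADA result needs a concurrent concentration.** The SAP classes PK by overall ADA status, a subject-level label. No planned analysis pairs an ADA result with a concentration from the same visit.
- **Nothing in the analysis could compensate.** A common-window partial AUC or an evaluability rule would address the between-group comparison, and extrapolation recovers part of AUC0-inf. The uncollected observation itself is still lost.

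**Conclusion.** This is a worthwhile, inexpensive improvement rather than an error that invalidates the analysis. Under the assumed model with a midway exit visit, the observed share of AUC0-inf rises by about 8-11 points after a last sample on Day 14, 5-9 after Day 28, 0-7 after Day 56 and under 3 after Day 84. The terminal slope gains a point. Cmax is little affected once the peak has passed. These figures depend on assumed half-lives and on where the exit falls between visits: nearer the next visit gains more, nearer the last one less.

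A reader might infer that an exit sample would cure bias from unequal dropout. It would not. A Day 28 leaver with a midway exit sample still has only 64-95% of AUC0-inf observed, against 97-100% for a completer. Such bias is lessened, and its size was not estimated because the documents give no dropout pattern by group. The PD benefit is smaller than the PK benefit, since SAP 12.3.3 derives no PD parameters.

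**What to change.** - Remove the PK and PD part from Table 1 footnote j and Table 2 footnote d, and from the SAP copies. Keep the exemption for the drug and alcohol screen.
- State that one PK and one PD sample are drawn at the early-discontinuation visit, with the actual time recorded.
- Reconcile the footnotes with Section 4.5 by stating that PK and PD are also drawn at any Day 112 visit a discontinued subject attends.
- In the SAP, use off-schedule PK samples in NCA at actual time, flag them in listings, and leave off-schedule PK and PD samples out of nominal-time summaries and mean plots.

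Cost: a short wording change in each document, about 10 mL more blood per attending subject at the exit visit, and flagging of the extra samples.
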